3.1.3. B/F/TAF Safety Analysis Set

The **B/F/TAF Safety Analysis Set** will include all participants who (1) are randomized into the study and (2) have received at least 1 dose of B/F/TAF study drug. All data collected up to 30 days after participants permanently discontinue study drug will be included in safety summaries, unless specified otherwise.

This is the primary analysis set for safety analyses.

3.2. Subject Grouping

Participants will be grouped into the following 3 groups:

- B/F/TAF: this group includes all participants randomized to the B/F/TAF group and who received at least 1 dose of B/F/TAF
- Delayed Switch to B/F/TAF: this group includes all participants randomized to the SBR group who switched to B/F/TAF at Week 24 and received at least 1 dose of B/F/TAF
- All B/F/TAF: all participants who received at least one dose of study assigned B/F/TAF (both immediate and delayed switch to B/F/TAF).

3.3. Strata and Covariates

Randomization was stratified by the baseline third agent ARV class at study entry (INSTI, NNRTI, PI or CCR5 antagonist).

If there are discrepancies in stratification factor values between the interactive web response system (IWRS) and the clinical database, the values recorded in the clinical database will be used to group participants for analyses.

3.4. Examination of Subject Subgroups

3.4.1. Subject Subgroups for Efficacy Analyses

No subgroup analyses for efficacy are planned for the final analysis.

3.4.2. Subject Subgroups for Safety Analyses

- 1) Incidence of all treatment-emergent AEs (TEAEs) will be analyzed for the following subject subgroups (also see Section 7.1.6):
 - Age (years): (a) < 50 and (b) ≥ 50
 - Sex at birth: (a) male and (b) female
- 2) Renal-related laboratory tests (ie, serum creatinine and eGFR_{CG}) will be analyzed for the following subgroups:
 - Baseline ARV Medication containing any of the following: rilpivirine (RPV), dolutegravir (DTG), ritonavir (RTV), cobicistat
 - Baseline ARV Medication not containing any of the following: RPV, DTG, RTV, cobicistat

3) Fasting metabolic laboratory tests will be analyzed for the following subgroups:

- Baseline ARV Medication containing TAF
- Baseline ARV Medication containing TDF
- Baseline ARV Medication not containing any of the following: TAF, TDF
- Baseline ARV Medication containing efavirenz (EFV)
- Baseline ARV Medication not containing EFV

4) Selected safety endpoints may be analyzed for the following subject subgroups (see Section 8.1 for details):

- Participants with HIV/HBV coinfection at baseline
- Participants with incident HIV/HBV coinfection while on study drug (if any)

5) Selected safety endpoints will be analyzed for the following subject subgroups (see Section 8.2 for details):

- Participants with HIV/HCV coinfection at baseline
- Participants with incident HIV/HCV coinfection while on study drug (if any)

3.5. Multiple Comparisons

No prespecified multiplicity adjustments are planned for confidence intervals (CIs) or statistical tests.

3.6. Missing Data and Outliers

3.6.1. Missing Data

A missing datum for a given study analysis window may be due to any of the following reasons:

- A visit occurring in the window, but data were not collected or were unusable
- A visit not occurring in the window
- A participant prematurely discontinuing from the study before reaching the window

In general, values for missing data will not be imputed, unless methods for handling missing data are specified.

For missing last dosing date of study drug, imputation rules are described in Section 3.8.1. The handling of missing or incomplete dates for adverse event onset is described in Section 7.1.5.2, and for concomitant non-ARV medications in Section 7.4.2.

3.6.2. Outliers

Outliers will be identified during the data management and data analysis process, but no sensitivity analyses will be done to evaluate the impact of outliers on efficacy or safety outcomes, unless specified otherwise. All data will be included in the analyses.

3.7. Data Handling Conventions and Transformations

Laboratory data that are continuous in nature but are less than the lower limit of quantitation or above the upper limit of quantitation will be imputed as follows:

- A value that is 1 unit less than the limit of quantitation will be used for calculation of descriptive statistics if the datum is reported in the form of “< x” (where x is considered the limit of quantitation). For example, if the values are reported as < 50 and < 5.0, values of 49 and 4.9, respectively, will be used for calculation of summary statistics. An exception to this rule is any value reported as < 1 or < 0.1, etc. For values reported as < 1 or < 0.1, a value of 0.9 or 0.09, respectively, will be used for calculation of summary statistics.
- A value that is 1 unit above the limit of quantitation will be used for calculation of descriptive statistics if the datum is reported in the form of “> x” (where x is considered the limit of quantitation). Values with decimal points will follow the same logic as above.
- The limit of quantitation will be used for calculation of descriptive statistics if the datum is reported in the form of “≤ x” or “≥ x” (where x is considered the limit of quantitation).

Logarithmic (base 10) transformations will be applied to HIV-1 RNA data for efficacy analyses. HIV-1 RNA results of ‘No HIV-1 RNA detected’ and “<20 cp/mL HIV-1 RNA Detected” will be imputed as 19 copies/mL for analysis purposes.

3.8. Analysis Windows

3.8.1. Definition of Study Day

Study Day 1/First Dose Date is defined as the day when the first dose of B/F/TAF was taken. The first dose date is the earliest nonmissing start date of B/F/TAF study drug recorded on the Study Drug Administration eCRF.

Study Days are calculated relative to Study Day 1. For events that occur on or after the Study Day 1 date, study days are calculated as (visit date minus Study Day 1 date plus 1). For events that occurred prior to Study Day 1, study days are calculated as (visit date minus Study Day 1 date).

Last Dose Date is defined as the maximum, nonmissing end date of B/F/TAF recorded on the Study Drug Administration eCRF and “Study Drug Permanently Discontinued” box checked for participants who prematurely discontinued study drug or completed study drug according to the Study Drug Completion eCRF.

For partial or missing last dose dates, please refer to the programming specifications for imputation rule details.

Last Study Date is the latest of the study drug start dates and end dates, the clinic visit dates, and the laboratory visit dates, including the 30-day follow-up visit date, for participants who prematurely discontinued study according to the Study Completion eCRF.

Baseline value is defined as the last value obtained on or prior to Study Day 1 for all assessments.

Note: for first dose date for SBR treatment group for listings, refer to the Week 48 SAP.

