6.4. Day 1 Assessments

The following evaluations are to be completed at the Day 1 Visit. **The Investigator must have confirmed eligibility before proceeding with the Day 1 visit.** Participants in Treatment Group 1 must complete all study procedures before being administered FDC of B/F/TAF:

- HIV Symptoms Distress Module Index and HIV Treatment Satisfaction Status (HIV-TSQs) are to be completed by the participant. Visual Analogue Scale (VAS) Adherence Questionnaire is to be completed by participants in Treatment Group 2 only. Participant is to read questionnaire by himself/herself and write/mark answers directly onto questionnaires.
- Review of AEs and changes in concomitant medications
- Complete physical examination (urogenital/anorectal exams will be performed at the discretion of the Investigator)
- Vital signs measurement (blood pressure, pulse, respiration rate, and temperature), including weight
- Obtain blood and urine samples as described in Sections 6.9.1 and 6.9.2.
- Dispense FDC of B/F/TAF for participants in Treatment Group 1

- Observed first dose administration of FDC of B/F/TAF in Treatment Group 1 as described in Section 5.3. If the participant has taken their prior regimen on Day 1, prior to the Study Visit, they should be instructed to take their first dose of B/F/TAF the following day and dosing can be confirmed by phone.
- Participants should be instructed to take FDC of B/F/TAF without regard to food. The participant should be counseled regarding the importance of adherence and taking their study medication at approximately the same time each day as directed by the Investigator.

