6.9.1. Blood Samples

- Blood sample collection for the following laboratory analyses will be performed at every study visit, unless otherwise specified:
 - Serum pregnancy test (all female participants). If the test is positive, the participant will not be enrolled (**Screening only**).
 - FSH test: Required for female participants who are <54 years old and have stopped menstruating for ≥ 12 months but do not have documentation of ovarian hormonal failure (**Screening only**)

— Chemistry profile: alkaline phosphatase, AST, ALT, total bilirubin, direct and indirect bilirubin, total protein, albumin, CPK, bicarbonate, blood urea nitrogen (BUN), chloride, creatinine, glucose, potassium, sodium, amylase, and Cystatin C

- Calcium, phosphorus, magnesium, amylase (reflex lipase testing is performed in participants with total amylase > 1.5 × ULN) (**Screening and Day 1 only**)

- Cystatin C (**Day 1 only**)

— Metabolic assessments: Fasting (no food or drinks, except water, at least 8 hours prior to blood collection) glucose and lipid panel (total cholesterol, HDL, direct LDL, and triglycerides) collected at **Day 1, Weeks 24, 48, and 72**.

- If the participant has not fasted prior to the visit, the visit may proceed, but the participant must return within 72 hours in a fasted state to draw blood for the metabolic assessments

— eGFR according to the Cockcroft-Gault formula:

Male:
$$\frac{(140 - \text{age in years}) \times (\text{wt in kg})}{72 \times (\text{serum creatinine in mg/dL})} = \text{creatinine clearance (CLcr)} \text{ (mL/min)}$$

$$\frac{(140 - \text{age in years}) \times (\text{wt in kg})}{72 \times (\text{serum creatinine in umol/L}) \times 0.6786} = \text{CLcr (mL/sec)}$$

Female:
$$\frac{(140 - \text{age in years}) \times (\text{wt in kg}) \times 0.85}{72 \times (\text{serum creatinine in mg/dL})} = \text{CLcr (mL/min)}$$

$$\frac{(140 - \text{age in years}) \times (\text{wt in kg}) \times 0.85}{72 \times (\text{serum creatinine in umol/L}) \times 0.6786} = \text{CLcr (mL/sec)}$$

— Hematology profile: complete blood count (CBC) with differential and platelet count

— CD4+ cell count and percentage (**Screening, Day 1, Weeks 24, 48, and 72, 30 Day Follow-up and ESDD**)

— Plasma HIV-1 RNA. Any subsequent HIV-1 genotype and phenotype testing will be performed as described in Sections [6.13.1](#) and [6.13.2](#).

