Appendix 2. Study Procedures Table

[figure not shown]
Study Procedure	Screening ^a	Day 1 ^b	End of Week ^c						Post Week 48 ^e	30 Day Follow-Up ^f	ESDD ^g
			4	12	24	28 ^d	36	48	Every 12 Weeks ^{cc}		
Informed Consent	X										
HIV Symptoms Distress Module		X	X		X	X		X			
HIV-TSQ ^h		X	X		X						
VAS Adherence Questionnaire ⁱ		X	X	X	X						
Medical History	X										
Concomitant Medications	X	X	X	X	X	X	X	X	X	X	X
Adverse Events	X	X	X	X	X	X	X	X	X	X	X
Complete/Symptom-Directed Physical Exam ^j	X	X	X	X	X	X	X	X	X	X	X
12-Lead ECG (performed supine)	X										
Height	X										
Weight	X	X	X	X	X	X	X	X	X	X	X
Vital Signs ^k	X	X	X	X	X	X	X	X	X	X	X
Urinalysis	X	X	X	X	X	X	X	X	X	X	X
Urine Pregnancy Test ^l		X	X	X	X	X	X	X	X	X	X
Serum Pregnancy Test ^l	X										
FSH Test ^m	X										
Chemistry Profile ⁿ	X	X	X	X	X	X	X	X	X	X	X
Metabolic Assessments ^o		X			X			X	X		
Estimated GFR	X	X	X	X	X	X	X	X	X	X	X
Hematology Profile ^p	X	X	X	X	X	X	X	X	X	X	X
Plasma HIV-1 RNA ^q	X	X	X	X	X	X	X	X	X	X	X
CD4+ Cell Count and Percentage ^r	X	X			X			X	X	X	X

Study Procedure	Screening ^a	Day 1 ^b	End of Week ^c						Post Week 48 ^e Every 12 Weeks ^{cc}	30 Day Follow-Up ^f	ESDD ^g
			4	12	24	28 ^d	36	48			
HBV Blood Panel ^s	X ^t							X ^t			
Plasma HBV DNA ^u		X			X			X		X	
HCV Serology ^v	X							X	X		
HIV-1 Genotype/Phenotype ^q										X ^q	
Plasma, Serum, and Urine Sample Storage ^w		X	X	X	X	X	X	X	X	X	
Whole Blood for HIV-1 DNA archive testing		X			X ^x						
CCI											
Obtain Screening Number	X										
Randomization ^z		X									
Study Drug Dispensation		X ^{bb}	X ^{bb}	X ^{bb}	X ^{aa}	X	X	X	X		
Study Drug Accountability			X ^{bb}	X ^{bb}	X	X	X	X	X	X	

- a Evaluations to be completed within 30 days prior to Day 1.
- b Participants should initiate dosing of study drug on the same day as the Day 1 visit.
- c All study visits are to be completed ± 6 days of the protocol-specified visit date (based on the Day 1 visit), unless otherwise specified.
- d Participants randomized to continue their baseline regimen will have an additional visit at Week 28.
- e At the study Week 48 Visit, participants who wish to continue on B/F/TAF will be given the option to receive FDC of B/F/TAF for up to an additional 24 weeks or until they have access to FDC of B/F/TAF, whichever occurs first, and attend study visits every 12 weeks (± 6 days of the protocol specified visit date) followed by a 30 Day Follow-Up Visit.

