- n Chemistry profile: alkaline phosphatase, AST, ALT, total bilirubin, direct and indirect bilirubin, total protein, albumin, CPK, bicarbonate, BUN, calcium, chloride, creatinine, glucose, phosphorus, magnesium, potassium, sodium, amylase, and Cystatin C. After Day 1, calcium, phosphorous, magnesium, and amylase (reflex lipase testing is performed in participants with total amylase $> 1.5 \times$ ULN) will not be collected. Analyses of glucose will be done as part of the fasting metabolic assessments, and not as part of the chemistry profile at Day 1, Weeks 24, 48, and 72. Cystatin C will only be collected at Day 1.
- o Metabolic Assessments will be performed at Day 1, Weeks 24, 48, and 72. Fasting (no food or drinks, except water, at least 8 hours prior to blood collection) glucose and lipid panel (total cholesterol, HDL, direct LDL, triglycerides). If the participant has not fasted prior to the visit, the visit may proceed, but the participant must return within 72 hours in a fasted state to draw blood for the metabolic assessments.
- p CBC with differential and platelet count.
- q HIV-1 genotype and phenotype testing for participants with confirmed virologic failure and HIV-1 RNA >200 copies/mL. Following virologic rebound, participants will be asked to return to the clinic (2-3 weeks later) prior to the next scheduled visit or at the next scheduled study visit for a HIV-1 RNA and HIV-1 resistance analysis (reverse transcriptase, protease, and integrase genotype and phenotype) blood draw. Based on the results of this testing, participants should be managed according to the Virologic Rebound Schema.
- r CD4+ Cell Count and Percentage to be collected at Screening and Day 1, and every 24 weeks thereafter, at Weeks 24, 48, and 72, in addition to the 30 Day Follow-up Visit and ESDD.
- s HBV blood panel will be performed at Screening and Week 48: HBsAg, HBsAb, HBcAb.
- t **For participants who are HBV co-infected (defined in Section 6.9.1):** The following HBV Blood panel will be conducted by the central laboratory: HBsAb, HBsAg (qualitative and quantitative), and HBeAg (if negative, reflex HBeAb).
For participants who are NOT HBV co-infected: The following HBV Blood panel will be conducted by the central laboratory: HBsAb, HBcAb, and HBsAg. Participants who are HBsAg or HBcAb positive will have a reflex test for HBV DNA (viral load).
- u **For participants who are HBV co-infected:** Plasma HBV DNA will be collected at Day 1, Week 24, Week 48 and ESDD.

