7.2.2.1. Treatment-Emergent Laboratory Abnormalities

Treatment-emergent laboratory abnormalities are defined as values that increase at least 1 toxicity grade from baseline at any postbaseline time point, up to the cutoffs specified at the start of Section 7.2.

If the relevant baseline laboratory value is missing, any abnormality of at least Grade 1 observed within the time frame specified above will be considered treatment emergent.

Fasting glucose and nonfasting glucose (including glucose results without a known fasting status) are graded based on different grading scales as specified in the protocol. Most participants had a nonfasting glucose at the Screening visit and a fasting glucose at the Day 1 visit; therefore, both a baseline nonfasting glucose and a baseline fasting glucose are available for most participants, and treatment-emergent laboratory abnormalities will be summarized for both nonfasting glucose and fasting glucose.

Both urine RBC based on microscopic examination, labeled as Hematuria (Quantitative), and urine blood based on a dipstick, labeled as Hematuria (Dipstick), are assessed and assigned a toxicity grade in this study. Hematuria (Quantitative) is a reflex test. Urine RBC based on microscopic examination or Dipstick will be presented in laboratory toxicity summary tables and listings.

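### Where the first B/F/TAF dose precedes a make-up fasting draw, a Group 1 participant has no fasting baseline and pre-existing lipid or glucose abnormalities count as treatment-emergent; the protocol conflicts with itself on which comes first

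*SAP*

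**What the plan says.** **Protocol.** Fasting glucose and lipids have four scheduled time points, none of them Screening: "Metabolic Assessments will be performed at Day 1, Weeks 24, 48, and 72" (Appendix 2, note o). If a participant arrives unfasted, "the visit may proceed, but the participant must return within 72 hours in a fasted state to draw blood for the metabolic assessments" (section 6.9.1; note o repeats it). Day 1 is not exempted.

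On dosing, Appendix 2 note b reads "Participants should initiate dosing of study drug on the same day as the Day 1 visit". Section 6.4 reads "Participants in Treatment Group 1 must complete all study procedures before being administered FDC of B/F/TAF", and its list of procedures includes the section 6.9.1 blood samples. For participants who have already taken their prior regimen that day, section 6.4 adds that "they should be instructed to take their first dose of B/F/TAF the following day and dosing can be confirmed by phone".

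**SAP.** Section 3.8.1 defines Study Day 1 as the date of the first B/F/TAF dose and states: "Baseline value is defined as the last value obtained on or prior to Study Day 1 for all assessments". Sections 3.8.3 and 7.2.1 repeat this cut-off. Table 3-2 ends the metabolic baseline window at Day 1 and runs the Week 24 window from Day 2 to Day 252. Section 7.2.2 does not grade non-fasting lipids, and section 7.2.2.1 grades fasting and non-fasting glucose on separate scales. The missing-baseline rule in section 7.2.2.1 begins "If the relevant baseline laboratory value is missing, any abnormality of at least Grade 1 observed" and classes such a value as treatment-emergent. Protocol 8.3 and 8.6.3 take the same approach. SAP Appendix 6, item 12, brings all graded post-baseline results into the toxicity summaries, not only those chosen for by-visit tables.

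**The concern.** The protocol's make-up provision and the SAP's baseline cut-off were not written with each other in mind. A sample taken to serve as the fasting baseline can fall after the first dose, and the SAP has no exception for it. The missing-baseline convention is meant for data that do not exist. Here a fasting value would exist, but the date rule turns it into the first on-treatment result.

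What is at stake is the reading of lipids and glucose after the switch, which belongs to the safety objective. A raised LDL carried over from the previous regimen could appear as an event on B/F/TAF. The final analysis does not summarize the SBR group's first 24 weeks (SAP 2.2), so no concurrent control column would show a similar artefact. The two columns shown side by side would also be affected differently: Group 1 would lose its fasting baseline, while Delayed Switch would use an old one.

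**Working it through.** The plan gives no figure on this point, so there is nothing to reproduce. The check applies the SAP's date rules and then sizes the effect under stated assumptions.

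**Step 1: which draws count as baseline.** For draws on or after the first dose, SAP 3.8.1 gives Study Day = draw date − first dose date + 1. A draw is baseline only if Study Day ≤ 1. The table takes draws at 24, 48 and 72 hours after a non-fasted Day 1 visit.

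| First B/F/TAF dose | 24 h draw | 48 h draw | 72 h draw |
|---|---|---|---|
| On the visit day (note b) | Day 2, post-baseline | Day 3, post-baseline | Day 4, post-baseline |
| Next day (section 6.4, prior regimen already taken) | Day 1, baseline | Day 2, post-baseline | Day 3, post-baseline |
| Not before the draw (section 6.4 read literally) | Day 1, baseline | Day 1, baseline | Day 1, baseline |

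The problem therefore depends on the order of dose and draw, which the protocol leaves in conflict.

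**Step 2: whether anything else can serve as baseline in Group 1.** Screening has no fasting panel. A non-fasting lipid result carries no grade. A non-fasting Screening glucose belongs to a different grading scale. In the post-baseline cells above, the fasting baseline is missing.

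**Step 3: consequences in Group 1.** The participant has no fasting change from baseline. Under SAP 7.2.2.1 every fasting value of Grade 1 or higher is treatment-emergent, and under Appendix 6, item 12, this includes the make-up draw itself. Appendix 4 of the protocol sets Grade 1 at 130 mg/dL for adult LDL, 200 mg/dL for total cholesterol and 110 mg/dL for fasting glucose. Triglycerides have no Grade 1 and are first graded at 500 mg/dL.

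**Step 4: Delayed Switch.** Study Day 1 for this group is the first B/F/TAF dose at Week 24. The fasting sample from randomization, even one drawn up to 72 hours late, comes before it. A participant not fasted at the switch visit and dosed before the make-up draw therefore normally has a baseline about 24 weeks old. Change over that time on the old regimen is then counted as change on B/F/TAF.

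**Step 5: size in Group 1, per laboratory test.** Excess treatment-emergent count = N × f × q, where

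- N = 320, the planned Group 1 size;
- f = share not fasted on Day 1 and dosed before the draw (assumed);
- q = share of those with a pre-existing Grade 1 or higher value on the given test (assumed).

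| f | q | N × f × q | Percentage points |
|---|---|---|---|
| 2% | 10% | 320 × 0.02 × 0.10 = 0.6 | 0.2 |
| 5% | 30% | 320 × 0.05 × 0.30 = 4.8 | 1.5 |
| 10% | 30% | 320 × 0.10 × 0.30 = 9.6 | 3.0 |
| 20% | 50% | 320 × 0.20 × 0.50 = 32 | 10.0 |

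These are upper figures for each pair of f and q, because some participants would have worsened by a grade anyway and been counted correctly.

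**The case against.** The strongest reply is that section 6.4 already settles the order. If all Group 1 procedures precede the dose, the fasting draw precedes it too, and no baseline is lost. The opposing text is an appendix footnote worded as a recommendation. This stands to the extent that a reader may not infer from the documents that non-fasted participants were in fact dosed first. It does not remove the point: the 72-hour provision has no Day 1 exception, and a site following it together with note b would draw after dosing.

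Second, counting abnormalities as emergent when baseline is missing is a prespecified convention for all laboratory tests, and it errs against the study drug. The final analysis is descriptive. Both statements are correct, and they limit the consequence. They do not make a pre-existing abnormality a new one.

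Third, Table 3-2 might suggest that a Day 2 to 4 draw would be reported as the Week 24 value. SAP 3.8.3 selects the record closest to nominal Day 168, so this happens only if no closer fasting record exists up to Day 252.

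Fourth, a reader might take the extreme corner, 32 of 320, as the effect, or combine all fasting tests into one percentage. The documents support neither. SAP 7.2.2.1 says most participants had a fasting glucose on Day 1, and SAP 7.2.2.2 summarizes by individual test.

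Fifth, making an on-treatment sample the main baseline could absorb early drug effect, and excluding participants without a baseline from the main table would contradict protocol 8.6.3. Both objections stand, and the fix below keeps those options to a sensitivity summary.

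**Conclusion.** The point holds conditionally. Sections 6.4 and 6.9.1 and Appendix 2 notes b and o do not agree on whether the fasting draw precedes the first dose. Where it does not, the SAP leaves the Group 1 participant without a fasting baseline and counts pre-existing Grade 1 or higher fasting lipid or glucose values as treatment-emergent. For Delayed Switch the baseline is normally old rather than missing, so the overcount does not apply there.

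With f of 5% to 10% and q of 30%, the excess is at most about 5 to 10 of 320 participants on a given test, or 1.5 to 3.0 percentage points. Neither share is in the documents. The mechanism is certain once dosing precedes the draw (or, with a next-day first dose, once the draw falls after that day); its frequency is unknown. Only the fasting lipid and fasting glucose summaries are affected, and no efficacy endpoint is. The separate Week 24 and Week 48 SAPs were not available, so whether the randomized comparison with SBR uses the same baseline rule cannot be judged.

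**What to change.** 1. Reconcile protocol 6.4, 6.9.1 and Appendix 2 notes b and o on whether the fasting draw precedes the first dose.
2. In SAP 3.8.1, 3.8.3, 7.2.1 and Table 3-2, state that a make-up fasting draw within 72 hours of the B/F/TAF start visit (Day 1, or Week 24 for Delayed Switch) is not a post-baseline or Week 24 value. All four places need the change, because each carries the cut-off or the window.
3. Report the number of Group 1 participants with no fasting baseline, and the number of Delayed Switch participants whose only fasting baseline is the Day 1 value.
4. Keep the rule in SAP 7.2.2.1 for the main table, in line with protocol 8.6.3. Add a sensitivity summary of the treatment-emergent fasting lipid and glucose rows and of the fasting changes from baseline, either excluding these participants or using the make-up draw as their baseline.
5. Record the change in SAP 7.8, which at present declares none.

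The cost is a protocol clarification and slightly more programming. If the make-up draw is used, the sensitivity baseline includes up to 3 days of B/F/TAF exposure for the participants concerned.
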